**Table 3. Estimated target number of HCPs per country**

Country	A Estimated Total Number of Invitation Emails*	B Estimated Number of Invitation Emails to HCP Prescribers	C Estimated Number of Invitation Emails to HCP Non- prescribers (10-	D Target Total Number of HCPs (4.4- 6.8% of column A)	E Target Number of HCP Prescribers (75-90% of column D)	F Target number of HCP Non- prescribers (10- 25% of column D)

		(75-90% of column A)	25% of column A)			
Austria	250-400	190-360	25-100	10-15	8-14	1-4
Switzerland	250-400	190-360	25-100	10-15	8-14	1-4
Germany	1250-1750	940-1580	125-440	50-70	38-63	5-18
Finland	100-150	75-135	10-40	5-10	4-9	1-3
France	1250-1750	940-1580	125-440	50-70	38-63	5-18
UK	1250-1750	940-1580	125-440	50-70	38-63	5-18
Hungary	250-400	190-360	25-100	10-15	8-14	1-4
Italy	1250-1750	940-1580	125-440	50-70	38-63	5-18
Netherlands	250-400	190-360	25-100	10-15	8-14	1-4
Sweden	100-150	75-135	10-40	5-10	4-9	1-3
Poland	100-150	75-135	10-40	5-10	4-9	1-3
Total	6000 - 9000	4500-8100	600-2250	up to 400	300-360	40-100

\* Estimated based on historical LiveTracker™ data.

Abbreviations: HCP = healthcare professionals; UK = United Kingdom

[figure not shown]
HCPs will provide consent and data will be anonymous for the Market Authorisation Holder (MAH).

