The Netherlands	OCT 2020 (reimbursed)	SEP 2020 (mail + website)	1,335 Oncologists / Haematologists + 631 hospital pharmacists + 350 clinical chemists (all HCPs in-training included) and 21 blood banks relevant societies for professionals	
UK	01 JUN 2020	APR-AUG 2020 (mail)	N=5061	
Poland		AUG-SEP 2020 (email, mail and website) Distribution of the revised version completed in Sep 2021	Physicians: haematologists (326), oncologists (705), specialists in transfusiology (97). National and regional consultants in haematology, oncology and transfusiology (48).	

Country	Actual/Estimated Launch Date	Implementation of EMs	Recipients	Comments
			Multiple myeloma treatment centres (53). Regional and field blood-donation centres (163).	
Germany	01 MAR 2021	JAN -MAR 2021 (mail and website)  Distribution of the revised version completed in June 2021	Oncologists and haematologists: 3655  Blood banks: 170	
Italy	29 MAR 2021	APR 2021 (email)	Haematologist, oncologists and scientific societies: 10 107	
Hungary	Planned NOV 2021	No distribution (product not yet launched)	To be provided later	

\* ATU: temporary authorisation for use ‘autorisation temporaire d’utilisation”

Abbreviations: BB = Blood Banks; EM = Educational Materials; HCP = healthcare professional; UK = United Kingdom

Since country inclusion is based on the date of launch and distribution of the educational materials, target population size, and representativeness of Europe, we will include, at minimum, the following five countries: France, Switzerland, Austria, Sweden, and the Netherlands. There will be a maximum of nine countries included in this study and the other potential countries include (but are not restricted to): Germany, Finland, United Kingdom (UK), Italy, Poland and Hungary. Also, the necessary Ethics/Regulatory requirements to conduct this study may generate some changes in this list.

Current countries listed are the ones with educational materials expected to be implemented by the end of 2021 (Table 1) as data collection will occur in each country 12-18 months post-implementation. The following EU countries cannot participate because SARCLISA (isatuximab) will not be marketed or educational materials will not be implemented by the end of 2021 in order to complete data collection by Q1 2023: Bulgaria, Cyprus, Estonia, Greece, Ireland, Latvia, Lithuania, Spain and Romania.

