**Table 2. LiveTracker™ haematologist and haemato-oncologist panels in each country.**

	Total Number of HCPs
Austria	538
Switzerland	1,135
Germany	4,696
Finland	156
France	3,549
UK	4,061
Hungary	120
Italy	3,298
Netherlands	647
Sweden	594
Poland	288
Total	19,082

Abbreviations: HCP = healthcare professional; UK = United Kingdom

HCP prescribers (haematologist/onco-haematologist) and non-prescribers (HCPs working in the blood banks/transfusion centres) will be recruited the same way through the LiveTracker™ panel. From the overall country-specific list of HCPs, invitation e-mails will be sent to HCPs to explain the objective of the study and their expected involvement, as well as provide a link to the electronic survey.

To maximise the response rate if the objective of 400 HCPs is not reached, multiple reminders will be sent. If recruitment rate is low after three reminders, we may consider different strategies including broadening the inclusion criteria to also include any HCPs who have prescribed other anti-CD38 therapy (prescribers) or who have provided blood products for a

patient treated with other anti-CD-38 therapy (non-prescribers). This change would be implemented after a protocol amendment is approved.

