To minimise selection bias, the number of HCPs is targeted based on the combination of the country population, target population (haematology and haemato-oncology centres and blood banks), and date of distribution of educational materials. Since this survey is targeting HCPs instead of patients, this recruitment approach will reflect the proportion of HCP prescribers/non-prescribers within these countries. Approximately 400 HCPs will be included in this study. It is expected that the European Union countries with a large population will have a greater number of HCPs included in the study compared to countries with a smaller population. In addition, the number of HCPs included per country will vary based on the volume of distribution of educational materials for each country. Recruitment strategy for HCPs will vary among countries as the aim will be to recruit HCPs who properly represent the HCP specialities and practice settings where educational materials are distributed in each country. Additional factors that will be considered during recruitment, in efforts for representativeness, include recruiting HCPs from different regions in each country, and recruiting HCPs with varying numbers of patients treated with isatuximab.

The final response rate is estimated to be 4.4%-6.8% based on historical LiveTracker™ data (17% of HCPs will respond to communication emails, and of those who respond, approximately 26% to 40% will be eligible and will complete the survey). In order to obtain close to 400 completed questionnaires, a total of approximately 6,000 to 9,000 invitation emails will be sent (it varies among country and will be adjusted based on the response rates of each country and each types of HCPs).

These invitation emails are planned to be sent using a stratified random sampling method, however, further random sampling steps after the initial email is likely not feasible since the goal is to maximize responses. A few reasons it is not feasible include 1) the low numbers of HCPs in some countries; 2) the low expected response rate (4.4%-6.8%).

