## 9.5 Study Size

The proportions of interest (p) here are the proportions of HCPs knowledgeable and adherent to the aRMMs. As the proportion of interest (p) is not known at the time of this document, we may consider it to be 50% (maximum uncertainty). Such a hypothesis yields the most conservative (largest) sample size. Based on a minimum level of precision of 5%, the minimum required sample size would be 384 for precision levels of 5% for the overall population. The sub-populations of interest will include prescribers (75% to 90%) and non-prescribers (10% to 25%) but the study is not powered for the analysis by sub-population.

Of note, similar aRMMs were distributed to HCPs in Europe after the market authorisation was granted to the first-in-class compound (daratumumab). Based on the information published in February 2021, a total of 408 participants completed the questionnaires.

In order to obtain 400 completed questionnaires in our study, it is estimated that approximately 6,000 to 9,000 HCPs will be approached. This is based on the details provided in [section 9.2.3](#).

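### Table 3 does not add up: its country targets sum to 255–370 HCPs (at most 350 for the nine countries allowed), short of the stated 384 and 400, although recruitment is not shown to be infeasible

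*Protocol*

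**What the plan says.** Section 9.5 gives the size requirement: "the minimum required sample size would be 384 for precision levels of 5% for the overall population", taking the proportion as 50%, and plans for 400 completed questionnaires. Section 9.2.3 repeats the aim: "Approximately 400 HCPs will be included in this study". It also gives the yield: "The final response rate is estimated to be 4.4%-6.8% based on historical LiveTracker™ data", being 17% who respond times 26% to 40% who are eligible and complete. From this it derives 6,000 to 9,000 invitation emails.

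Table 3 spreads these figures over 11 candidate countries. Column A holds the emails. Column D is headed "Target Total Number of HCPs (4.4- 6.8% of column A". Columns E and F split D into prescribers and non-prescribers. The total row reads 6,000–9,000 emails, up to 400 HCPs, 300–360 prescribers and 40–100 non-prescribers.

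Section 9.2 limits participation: "There will be a maximum of nine countries included in this study". Five are fixed: France, Switzerland, Austria, Sweden and the Netherlands. Table 2, which lists the "haematologist and haemato-oncologist panels in each country", shows 120 HCPs for Hungary.

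**The concern.** Table 3 is the only place where the overall requirement becomes numbers per country, so it should agree with the response rate, the country limit, the panel sizes and its own total row. It fails on all four. Anyone who sets fieldwork targets from the country rows would be working to fewer completed questionnaires than Section 9.5 needs. The total row hides this because it was not obtained by adding the rows. What is at stake is the stated 5-point precision, and a reader's ability to see how far precision depends on which countries join.

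**Working it through.** **Inputs.** Table 3 rows (emails; D; E; F):

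- Germany, France, UK, Italy, each: 1,250–1,750; 50–70; 38–63; 5–18
- Austria, Switzerland, Hungary, Netherlands, each: 250–400; 10–15; 8–14; 1–4
- Finland, Sweden, Poland, each: 100–150; 5–10; 4–9; 1–3

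The 384, p = 50% and 5 points come from Section 9.5. The Abstract attaches the 384 to each sub-population; the overall reading in Section 9.5 is more lenient and is used here. Section 9.5 gives no confidence level; I assume 95% two-sided.

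**1. The plan's own figures.** n = 1.96² × 0.25 / 0.05² = 384, so the requirement reproduces. The 400 also reproduces, but only from the headline email totals: 6,000 × 6.8% = 408 and 9,000 × 4.4% = 396. The totals of E and F are 75–90% and 10–25% of 400. The total row is therefore a top-down split of 400.

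**2. Sum of the rows, all 11 countries.**

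- A: 4×1,250 + 4×250 + 3×100 = 6,300; 4×1,750 + 4×400 + 3×150 = 9,050 (printed 6,000–9,000)
- D: 4×50 + 4×10 + 3×5 = 255; 4×70 + 4×15 + 3×10 = 370 (printed up to 400)
- E: 4×38 + 4×8 + 3×4 = 196; 4×63 + 4×14 + 3×9 = 335 (printed 300–360)
- F: 4×5 + 4×1 + 3×1 = 27; 4×18 + 4×4 + 3×3 = 97 (printed 40–100)

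**3. Nine-country limit.**

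- Best permitted nine (the five fixed plus Germany, UK, Italy, Hungary): D = 200 + 40 + 5 = 245 to 280 + 60 + 10 = 350. No choice of nine rows exceeds 350.
- Smallest nine containing the five fixed (adding Finland, Poland, Hungary and one large country): D = 85 + 5 + 5 + 10 + 50 = 155 to 125 + 10 + 10 + 15 + 70 = 230.
- The five fixed alone: 85–125.

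At the upper limits the shortfall against 384 is 14 with all 11 countries and 34 with the best nine. Against 400 it is 30 and 50.

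**4. Rate actually used in column D**, matching lower limit to lower and upper to upper:

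- Four large countries: 50/1,250 = 4.0% and 70/1,750 = 4.0%
- Four mid-size countries: 10/250 = 4.0% and 15/400 = 3.75%
- Finland, Sweden, Poland: 5/100 = 5.0% and 10/150 = 6.7%

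Eight of the 11 rows lie below the labelled 4.4–6.8%.

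**5. Column A at the stated rate, best nine.** Emails are 5,000 + 1,000 + 100 = 6,100 to 7,000 + 1,600 + 150 = 8,750. With the plan's pairing (few emails with the high rate, many with the low), 6,100 × 6.8% = 415 and 8,750 × 4.4% = 385. The 385 has no slack. If Hungary sends 120 prescriber and 100 non-prescriber emails, the ceiling is 8,750 − 400 + 220 = 8,570, giving 377. With Finland or Poland in place of Hungary it is 8,500, giving 374.

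**6. Hungary.** Table 3 assigns 190–360 prescriber emails; the panel holds 120. No other country's prescriber emails exceed its Table 2 panel.

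**7. Precision from the tabulated targets**, half-width = 1.96 × √(0.25/n):

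| Country set | n | Half-width (points) |
|---|---|---|
| Requirement | 384 | 5.0 |
| All 11 | 370–255 | 5.1–6.1 |
| Best nine | 350–245 | 5.2–6.3 |
| Smallest nine with the five fixed | 230–155 | 6.5–7.9 |
| Five fixed only | 125–85 | 8.8–10.6 |

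**The case against.** Column D is labelled an estimate, and nothing in the protocol makes it a quota at which a country closes. The operative aim is about 400 overall. Section 9.2.3 allows emails to be adjusted to the response rates seen, provides for repeated reminders if 400 is not reached, and mentions broader eligibility by amendment after that. A reader might infer that fieldwork will end below 384. The documents do not support that: step 5 shows the invitation volume is about right for the best nine, and the error sits mainly in the country cells of D, E and F. This stands in full.

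The loss at the top of the best nine is small, and smaller still at the 80% threshold: 1.96 × √(0.16/350) = 4.2 points. All analyses are descriptive, so no error rate depends on it. This also stands, but only for that country set at its upper limit.

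A reader might also blame the table for a very small non-prescriber group (lower limits of column F: 20 + 4 + 1 = 25 for the best nine, against a printed 40). Section 9.5 already says the study is not powered by sub-population, and Section 9.2.3 treats the 10–25% share as a minimum. The table misstates the expected number; it does not create the limitation.

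For Hungary, Section 9.2.3 adds distribution lists and a blood-bank panel under construction, so a flat limit of 120 on all its emails would be wrong. Table 1, however, records no distribution there yet and leaves recipients to be supplied.

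What the objection does not remove is the inconsistency. Adjusting emails leaves the country targets wrong, and Section 9.2.3 relies on country targeting to limit selection bias. Filling the gap ad hoc changes the country mix.

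**Conclusion.** Table 3 is internally inconsistent. The totals of D, E and F are not the sums of their rows, more countries are counted than may take part, eight of 11 rows depart from the labelled rate, and Hungary's prescriber emails exceed its panel. As tabulated, the targets fall short of 384 and 400 for every permitted country set. The size of the shortfall depends on the choice of countries: slight for the best nine at their upper limits, material for smaller sets. This calls for correcting the table and the precision statement. It is not evidence that the study cannot recruit 384.

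The sums are exact. The half-widths assume 95% confidence, p = 50% and simple random sampling. The 385–415 range assumes the email and rate limits are paired inversely, as the plan's own 6,000–9,000 implies.

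**What to change.** - Rebuild Table 3 for the nine or fewer countries actually used, and make every total the sum of its rows.
- Derive column D from column A at the stated 4.4–6.8%, and say how the ends are paired. For Germany, inverse pairing gives 1,750 × 4.4% = 77 to 1,250 × 6.8% = 85; like-with-like pairing gives 55–119. Neither is 50–70.
- Limit Hungary's prescriber emails to its available panel plus any distribution list that exists by then.
- Set invitation ceilings for the chosen countries so that the lowest stated rate still yields 384: 384/0.044 = 8,727 emails, within the planned 9,000. Draw on the unused panel in whichever of Germany (4,696), the UK (4,061), France (3,549) and Italy (3,298) take part; Table 3 assigns each at most 1,580 prescriber emails.
- Otherwise, restate the precision in Section 9.5 for the country set chosen, using the half-widths in the table above. For the five confirmed countries this is the likely route: their Table 2 panels total 538 + 1,135 + 3,549 + 647 + 594 = 6,463, below 8,727 before any blood-bank or distribution-list contacts are added.

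The cost is a corrected table and a sentence in Section 9.5. For the best nine, the extra emails are none if Hungary's row can be filled, and about 160 to 230 if it is reduced or replaced (8,727 − 8,570 = 157; 8,727 − 8,500 = 227). Smaller country sets would need more. The overall target of 400 is unchanged.

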#### 9.2.4 Study Period

The GVP Module XVI guidelines(7) recommend that effectiveness of aRMMs is measured within 12 to 18 months after implementation of the educational material(s). As a result, data collection would start no earlier than Q3 2021 and no later than Q2 2022. Based on the estimated launch sequence that will be progressive throughout 2021, data collection will most likely take place until at least the end of 2022 and potentially up to Q1 2023.

Figure 1 presents the study design schematic, including periods of survey data collection.

**Figure 1. Study Design Schematic**

### 9.3 Variables

Variables related to the following HCPs' characteristics will be collected:

- Participation (e.g. response rate)
- Practice setting
- Receipt of the educational materials
- Knowledge of each safety messages
- Behaviour with respect to the actions listed in the educational materials

Please refer to [Appendix C](#) for detailed survey questionnaire.

#### 9.3.1 Practice setting and selection criteria

The following will be collected from the LiveTracker™ database:

- Country and region of practice
- Primary specialty

- Primary setting of practice (e.g. blood bank, transfusion centre, private practice, local hospital, regional hospital, university hospital, private hospital)

The following will be used to assess the selection criteria and will be collected via the survey questionnaire:

- Number of patients to whom the physician has prescribed isatuximab in the past year
- Length of time since last prescription of isatuximab

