### **9.3.2 Implementation**

All HCPs:

- Reception of the education materials (brochure and maybe Patient Card depending on the type of HCPs).

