**PI – List Drop Down.**

PI- Drop down with list of subspecialties; show Medical Oncology subspecialties if P1a= Medical Oncology; show Hematology subspecialties if P1a= Haemato-oncology/onco-haematology; show Internal medicine subspecialties if P1a= Internal medicine

[DP:1]

-----Page Break-----

**Px.** For the treatment of Multiple Myeloma, please indicate your level of adoption of **isatuximab**.

- Prescribe on a regular basis
- Have prescribed at least once
- Are aware but have never prescribed
- Are not aware

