**Questions for Prescribers**

PI- Show if Px= “Prescribe on a regular basis” or “at least once”

- 1 **Have you received the educational material from Sanofi regarding the minimization of risk associated with isatuximab?**
  - Yes
  - No

PI- List drop down

[DP:1]

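### Two prescribing variables that section 9.3.1 assigns to the questionnaire have no item in Appendix C, and receipt of the materials is asked only as one pooled Yes/No

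*Protocol*

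**What the plan says.** Section 9.3.1 divides HCP characteristics by source. Country, specialty and setting come from the LiveTracker database. A second group is introduced with "The following will be used to assess the selection criteria and will be collected via the survey questionnaire". It has two entries: "Number of patients to whom the physician has prescribed isatuximab in the past year" and "Length of time since last prescription of isatuximab".

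Section 9.2.3 gives patient numbers a further role. Among the factors to be considered for representativeness it lists "recruiting HCPs with varying numbers of patients treated with isatuximab".

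On receipt, section 9.3 lists "Receipt of the educational materials" and section 9.3.2 expands this to "Reception of the education materials (brochure and maybe Patient Card depending on the type of HCPs"). Section 9.3 refers the reader to Appendix C for the detailed questionnaire. There, Px asks the respondent to "please indicate your level of adoption of" isatuximab. Q1 for prescribers asks "Have you received the educational material from Sanofi regarding the minimization of risk associated with isatuximab", answered Yes or No. The non-prescriber Q1 is almost identical.

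**The concern.** A protocol that names a variable and its source should have an instrument that collects it. Two named variables have no corresponding question, and a statistical analysis plan cannot supply answers that were never requested. The plan provides no later remedy, because section 9.9 says HCPs will not be contacted again to clarify or revise their responses.

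Three descriptive uses are affected.

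- **Representativeness.** The spread of isatuximab patient numbers, an aim of section 9.2.3, could be judged only roughly from Px.
- **Description of participants.** Section 9.7.3 makes the participants' characteristics, including the inclusion criteria, the first analysis step, and 9.3.1 ties these two variables to the selection criteria.
- **Comparison by score.** Section 9.7.6 compares responders who did and did not reach the correct-answer thresholds. Volume and recency of use would be natural characteristics to include.

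On receipt, a prescriber who had one material but not the other has no accurate answer to Q1. Prescriber Q9 and Q10 concern the Patient Card, yet the survey cannot show whether that respondent received it. A respondent who does not remember must still choose Yes or No, since section 9.6.1 treats a survey as valid only when every question is answered. Those guesses carry into the received versus not-received comparison in 9.7.6.

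**Working it through.** The plan gives no figure to reproduce, and the point rests on no sample-size formula. The check compares sections 9.3 to 9.3.2 with every item in Appendix C: P0, P0a, P1, P1a, P1b, Px, Px0, Px1, Px2, prescriber Q1 to Q10 and non-prescriber Q1 to Q7.

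| Variable | Stated source | Nearest item in Appendix C | Result |
|---|---|---|---|
| Isatuximab patients in the past year | Questionnaire (9.3.1) | Px: regular prescriber, at least one prescription, aware but never prescribed, not aware | No count and no one-year window |
| Time since last prescription | Questionnaire (9.3.1) | Px, as above | No date or interval |
| Receipt of materials | Listed in 9.3 and 9.3.2 | Q1, Yes/No, both HCP types | Collected, but pooled |

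**Items outside Px.** P0 to P1b cover country and specialty, and Px0 and Px1 cover setting. Px2 grades the supply of blood products as regular, at least once or never, again without count or date. The remaining questions are Q1 on receipt and the knowledge and behaviour items. None asks for a number of patients or a time.

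**Extent.** Both of the questionnaire variables in 9.3.1 lack an item. They concern prescribing, so the gap applies to all prescribers. Table 3 targets 300 to 360 of these (75% × 400 = 300; 90% × 400 = 360).

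**Other sources.** Section 9.2.3 says the LiveTracker profiling survey covers caseload. It does not say that this is isatuximab-specific, and 9.3.1 assigns the two variables to the questionnaire rather than the database.

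**Eligibility.** The inclusion criteria in 9.2.2 require at least one prescription, or at least one supply of blood products to a treated patient. The screening rule in Appendix C decides both from Px and Px2. Neither missing variable is needed.

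**The 80% criteria.** Section 9.7.4 builds these on the key knowledge question, five of seven prescriber behaviour items and two of three non-prescriber behaviour items. Neither the missing variables nor Q1 enters them.

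**Receipt.** Section 7 identifies the materials as a brochure for both HCP types and a Patient Card passed to patients by their HCPs. Section 9.4 includes a don't-know option in its example answer formats, whereas Q1 offers only Yes and No. The 9.7.6 comparison can be run on the pooled answer. A brochure-versus-card breakdown cannot.

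**The case against.** The strongest reply is that little depends on the gap. The stated purpose of the two variables is to assess selection, which Px and Px2 already do. No analysis in 9.7.6 names volume or recency. Varying patient numbers is a factor to consider during recruitment, not an endpoint, and Px separates regular prescribers from the rest. All of this stands and limits the point to descriptive detail. It does not remove the contradiction: the protocol promises data that its own instrument does not request.

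A second reply is that Appendix C may not be final. Section 9.4 foresees user acceptance testing and pilot interviews with two HCPs per country, and some answer options still carry question marks. A reader might infer that loss of the data is already certain. The documents do not support that, because the items can still be added. What they show is the result if Appendix C is fielded as it stands.

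A reader might also infer that receipt is not collected, or that the protocol promised receipt of each material separately. Neither holds. Section 9.3 speaks of the materials collectively, the parenthesis in 9.3.2 is hedged, and Q1 covers both HCP types.

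Nor does Objective 1 fail. Section 9.7.4 describes implementation at country level, and Table 1 already records dates and recipients for most candidate countries, with distribution channels for many. Respondents' recall of each material would add to this, but Objective 1 is not stated to depend on it.

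Finally, time since last prescription would not show which version of the brochure a respondent had seen, so the gap should not be argued on that ground.

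**Conclusion.** The inconsistency is confirmed. Both questionnaire variables in 9.3.1 lack an item in Appendix C, so prescribers could not be described by isatuximab patient numbers or time since last prescription beyond the undated categories of Px. Receipt is available only as one pooled Yes/No. That prevents reporting by material and makes unsure respondents guess, to an extent the documents give no basis for estimating.

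The consequence is moderate. Eligibility, the 80% criteria and the ability to run the received versus not-received comparison all survive. It should be corrected before launch, but it does not threaten the main conclusion of the study. The verdict assumes that Appendix C is fielded as printed and that LiveTracker's caseload field is not isatuximab-specific; the protocol does not say that it is.

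**What to change.** Before launch:

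1. Add two banded items to the prescriber stream of Appendix C: number of patients prescribed isatuximab in the past 12 months, and time since last prescription. Alternatively, delete both from 9.3.1 and revise the representativeness aim in 9.2.3 so that it does not rely on patient numbers that are not collected.
2. Split Q1 into receipt of the brochure and, where it applies to the HCP type, receipt of the Patient Card. Give each the answers Yes, No and Do not recall. Keep the received versus not-received analysis in 9.7.6.

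**Cost.** Three to four short closed items: two new items plus the two halves of Q1, one of which replaces the existing question, so a prescriber answers at most three more (2 + 2 − 1 = 3). Where the Patient Card does not apply, a non-prescriber answers no extra question. An estimated one extra minute per respondent is realistic for items of this kind. Scaling the plan's 15 minutes over the roughly 15 items a prescriber sees (P0, P1, Px, Px0, Px2 and Q1 to Q10) would give three minutes at most. Translations and pilot interviews would need to cover the added items.
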